7.2. Treatment Assignment

Patients who have an indication to be implanted with a LUX-Dx ICM based on the product's labelled indications, and who meet study-specific eligibility criteria will be considered for enrollment. To be enrolled in the study, subjects must meet all study -specific eligibility criteria and sign the study-specific Informed Consent Form (ICF).

There is no randomized treatment assignment in this study. The study is considered "all comers" for patients who are eligible.

7.3. Justification for the Study Design

The objective of the LUX-Dx PERFORM Study is to collect data in a clinical setting reflecting real-world usage of the LUX-Dx ICM. Therefore, a prospectively enrolled, observational, post-market study design was determined to be appropriate. Subject enrollment requirements are supported by the following:

- A sample size of 227 subjects will be required to power the first primary safety endpoint analysis (acute endpoint), and 226 subjects will be required to power the second primary safety endpoint (chronic endpoint).
- The Holter study group is expected to enroll approximately 600 subjects, including approximately 300 subjects from the "AF management, Post-AF ablation, or Suspected AF" subgroup, and approximately 300 subjects from the other 2 subgroups ("Syncope" and "Cryptogenic stroke"). The distribution of the device indications is desired to generate at least 100 subjects with a detected AF episode during the Holter

	Form/Template 92120219_Rev/Ver D			
Confidential	LUX-Dx PERFORM Protocol, 92557593, Rev/Ver C			
	Page 25 of 66			
monitoring period. Refer to Section 11.1.2.2 for rationales of the sample size				

requirement in the Holter study.

Refer to Section 11 for details of overall study sample size discussion.

8. Subject Selection

8.1. Study Population and Eligibility

Subjects should be selected from the general patient population indicated for ICM implantation per BSC labeled indication and are accessible to the Investigators. The LUX-Dx ICM System is indicated to monitor and record S-ECG for the clinical evaluation and diagnosis of cardiac arrhythmias in patients who have: 1) a known heart condition, 2) are at risk of developing an abnormal heart rhythm, or 3) have symptoms that may suggest a cardiac arrhythmia (e.g. dizziness, palpitations, syncope, chest pain, and/or shortness of breath). The Investigators are responsible for screening all potential subjects and selecting those who meet the eligibility for the study as described in Section 8.2 and 8.3 below.

8.2. Inclusion Criteria

Patients who meet all of the following criteria (see Table 8-1) may be given consideration for inclusion in this clinical investigation, provided no exclusion criteria (see Section 8.3) are met.

Form/Template 92120219_Rev/Ver DConfidentialLUX-Dx PERFORM Protocol, 92557593, Rev/Ver CPage 26 of 66

Inclusion Criteria	• Patient is indicated to be implanted with the LUX-Dx ICM for one of the following reasons (grouped in three "Reason for Monitoring" subgroups):			
	 Cryptogenic stroke 			
	o Syncope			
	 AF management, Post-AF ablation, or Suspected AF 			
	• Patient is willing to enroll and be monitored in LATITUDE Clarity.			
	• Patient is willing and able to be followed remotely via the ICM patient mobile app.			
	• Patient is willing and capable of providing informed consent (which is not to include the use of a legally authorized representative (LAR) for documentation of informed consent) and agrees to participate in all protocol required activities.			
	• Patient is age 18 years or above, or of legal age to give informed consent specific to state and national law.			
	The following inclusion criterion is applicable for patients participating in the Holter study:			
	• Patient can tolerate the adhesive used in the Holter monitoring for an extended period of time.			

Table 8-1: Inclusion Criteria

8.3. Exclusion Criteria

Patients who meet any one of the following criteria (Table 8-2) may not take part in this clinical study.

	Table 0-2. Exclusion Criteria
Exclusion Criteria	• Patient is indicated for implantation of, or is currently implanted with an active implantable cardiac device (e.g., LVAD, ICD, CRT-D, PPM*).
	• Patient cannot tolerate a subcutaneous, chronically-inserted device due to medical condition.
	• Patient has a documented life expectancy of less than 12 months (per investigator's discretion).
	• Patient is known to be pregnant at the time of study enrollment (method of assessment upon investigator's discretion).
	• Patient is currently enrolled in another clinical study including
	observational studies/registries, unless prior written approval from BSC
	is obtained. Mandatory governmental registries are accepted for co- enrollment without approval by BSC.
	The following exclusion criteria are applicable for patients participating in the Holter study:
	• Patient has known allergies to the adhesive materials or hydrogel used in the extended Holter monitoring.
	• Patient has broken, damaged, or irritated skin over the chest area where the extended Holter monitor will be attached.
	*LVAD: Left Ventricular Assist Device; ICD: Implantable Cardioverter Defibrillator; CRT-D: Cardiac Resynchronization Therapy-Defibrillator; PPM: Permanent Pacemaker

Table 8-2: Exclusion Criteria

9. Subject Accountability

9.1. Point of Enrollment

Subjects will be considered enrolled into the study at the time of study-specific ICF execution. All subject enrollments will be counted against the enrollment ceiling for the study.

9.2. Enrollment Control

Approximately 600 to 827 subjects will be enrolled.

9.2.1. Enrollment Control of the "Safety Cohort" Subjects

The first 227 subjects are required to meet the sample size requirement set for the study's primary safety endpoint - acute. These subjects will be asked to participate in the Holter study, but will not be required to join if subject declines.

9.2.2. Enrollment Control of the Holter Study

Enrollment in the Holter study will also be controlled to ensure approximately 300 subjects are from the "AF management, Post-AF ablation, and Suspected AF" subgroup. This sample size is required to satisfy the data requirement for this objective.

It is expected that a total of approximately 600 subjects will be required to participate in the Holter study. BSC may determine that additional subjects will be needed to meet the requirement if data collected are deemed inadequate. In this case, site will continue to enroll Holter subjects until BSC communicates to all sites to stop enrollment.

9.2.3. Enrollment Control at Each Site

No single site may enroll greater than 90 subjects in the study without prior approval from BSC. Additionally, no single site may enroll greater than 34 subjects in the Safety Cohort (the first 227 subjects in the study) without prior approval from BSC.

9.3. Withdrawal

All subjects enrolled in the study shall be accounted for and documented including those subjects who withdraw prior to the 12-month electronic medical record (EMR) review. The reason(s) for withdrawal shall be reported on the End of Study Case Report Form (CRF). Reason(s) for withdrawal may include, but are not limited to:

- Subject found not meeting study's eligibility criteria
- Lost to follow-up
- Not able to re-establish device transmission after 90 days despite subject contact
- Subject choice to withdraw consent
- Investigator decision to withdraw the subject
- Subject is classified as Intent or Attempt as per Section 9.5
- The ICM is explanted or permanently disabled with all features programmed off
- Subject implanted with active therapy device (e.g. LVAD, ICD, CRT-D, PPM) even if the ICM remains implanted

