9.5. Subject Status and Classification

Enrolled subjects will be classified as follows:

Intent refers to a subject who has been enrolled in the study but then does not have local anesthetic administered in preparation for a LUX-Dx ICM implant procedure. The original ICF and enrollment documentation for intent subjects should be maintained in the study file. The Intent subjects must be withdrawn from the study and the End of Study CRF completed. If the Intent subject is withdrawn due to reason of eligibility violation, a protocol deviation is required. There are no follow-up requirements for intent subjects.

Attempt refers to a subject who has been enrolled in the study, has had local anesthetic administered in preparation for the implant procedure of a LUX-Dx ICM, but is not successfully implanted with the LUX-Dx ICM. Attempt subjects must be followed at least 30 days post implant attempt and all reportable adverse events associated with the LUX-Dx ICM or attempted implant procedure must be reported and followed to resolution, or closure of the event with ongoing or chronic status. The safety check attempts must be made between 30 days and 60 days after the attempted implant procedure. These subjects must be withdrawn from the study and the End of Study CRF completed after the resolution of all reportable adverse events and the completion of the safety check.

Implant refers to a subject who has been enrolled in the study and is successfully implanted with the LUX-Dx ICM. These subjects are followed in accordance with the protocol and included in all applicable analyses.

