11.2. General Statistical Methods

11.2.1. Analysis Sets

Data from Implant and Attempt subjects will be used for each objective and endpoint as appropriate. Further details will be outlined in the Statistical Analysis Plan.

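### Section 9.3 lets an implanted subject be withdrawn as ineligible with no required safety check, so later complications are censored out of the safety endpoints (minor)

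*Combined protocol and SAP*

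**What the plan says.** Section 9.3 (Withdrawal) introduces an open list with "Reason(s) for withdrawal may include, but are not limited to". The list contains "Subject found not meeting study's eligibility criteria" and, separately, "Investigator decision to withdraw the subject". Neither is tied to a subject's classification or to time since implant. The same section requires that "All subjects enrolled in the study shall be accounted for and documented including those subjects who withdraw prior to the 12-month" EMR review.

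Section 9.5 (Subject Status and Classification) deals with ineligibility in one place, for subjects who never received local anesthetic: "If the Intent subject is withdrawn due to reason of eligibility violation, a protocol deviation is required". For Implant subjects it says: "These subjects are followed in accordance with the protocol and included in all applicable analyses".

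Section 11.2.1 (Analysis Sets) says "Data from Implant and Attempt subjects will be used for each objective and endpoint as appropriate" and leaves the detail to the SAP. Sections 11.1.3.2 and 11.1.4.2 estimate the 30-day and 12-month complication-free rates by Kaplan-Meier. Each compares a one-sided 97.5% log-log lower limit with its goal, 94% and 93% respectively.

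A safety check 30 to 60 days after the event is required for Attempt subjects (9.5). Section 10.9 requires one after explant and where the device has been disabled or permanently programmed off.

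**The concern.** The documents do not say what happens to a subject who already carries the device and is then found not to have met the criteria. Section 9.3 permits withdrawal. None of the safety checks in 9.5 or 10.9 covers someone who leaves for this reason with a functioning device in place. The 6- and 12-month EMR and telephone reviews would stop although the subject is still exposed to the device under study.

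Kaplan-Meier assumes that those who leave have the same later risk as those who stay. That assumption could fail here. One exclusion criterion in 8.3 is "Patient cannot tolerate a subcutaneous, chronically-inserted device due to medical" condition, and 18.2.2 lists local tissue reaction, erosion and foreign body rejection as anticipated events. A site that sees an early, mild reaction might conclude that the criterion had never been satisfied. If the subject is withdrawn and the device is explanted for that reaction months later, the explant is not counted. The estimated complication-free rate is then too high, in the direction of meeting the goal. This path from reaction to eligibility finding is an inference; no section describes it.

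**Working it through.** **1. The sections side by side**

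| Subject | Ineligibility addressed? | Safety check required? |
|---|---|---|
| Intent | Yes, 9.5: withdrawal plus deviation | No follow-up required |
| Attempt | Not addressed | Yes, 9.5 |
| Implant, explanted | Not applicable | Yes, 10.9 |
| Implant, device disabled or programmed off | Not applicable | Yes, 10.9 |
| Implant, working device, found ineligible | Only through the general list in 9.3 | None stated |

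The last row is the gap.

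**2. The plan's own figures**

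Section 7.3 gives 227 subjects for the acute endpoint and 226 for the chronic one. These cannot be reproduced, because the expected rates, power and attrition are not in the available text. This point does not dispute them.

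**3. How close to the boundary the tests operate**

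Inputs: goals of 94% and 93% and the one-sided 97.5% log-log limit (11.1.3.2, 11.1.4.2); n = 227 (7.3, 11.1.5). Assumption: all 227 are implanted and followed to the time point.

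With e events and no censoring:

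- S = 1 − e/n
- Greenwood sum G = e / [n(n − e)]
- se = √G / |ln S|
- lower limit L = S^exp(1.96 × se)

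Worked case, e = 8: S = 219/227 = 0.96476; G = 8/(227 × 219) = 0.00016092; se = 0.012686/0.035878 = 0.3536; L = 0.96476^2.000 = 0.9308.

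| Endpoint | Goal | Events of 227 | Lower limit | Result |
|---|---|---|---|---|
| 30 days | 94% | 6 | 94.21% | met |
| 30 days | 94% | 7 | 93.64% | missed |
| 12 months | 93% | 8 | 93.08% | met |
| 12 months | 93% | 9 | 92.52% | missed |

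With n = 226 at 12 months, 8 and 9 events give 93.05% and 92.49%: the same cut-off.

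**4. One event lost through censoring**

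Suppose 9 of 227 subjects truly have a complication within 12 months. One of them is withdrawn event-free near day 40 and has the complication afterwards. Eight events are observed, and the risk set falls by one from day 40. With event times spread evenly over the year (an assumption), L is about 93.05%. The timing matters little: if all eight observed events precede the withdrawal the limit equals that for 8 of 227 (93.08%), and if all follow it the limit equals that for 8 of 226 (93.05%). A result that should miss the goal meets it.

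**5. Direction**

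The gain arises only if a later event is lost. Early withdrawal of subjects who would have stayed event-free shrinks the risk set and works slightly the other way. With 8 events and five such subjects gone before the first event, n is effectively 222, S = 214/222 = 0.96396 and L = 92.92%, which misses the goal. The concern is therefore informative withdrawal, not withdrawal as such.

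**6. Which endpoint**

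The 30-day estimate changes only if withdrawal precedes day 30. Table 10-1 schedules no subject contact after implant until the 2-month (±30 days) Holter visit, and the first 227 subjects may decline the Holter study (9.2.1). Most opportunity therefore falls between day 30 and 12 months.

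**The case against.** Four points on the other side carry weight.

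- **Withdrawal is not deletion.** A reader might infer that implanted subjects can be taken out of the safety endpoints. The documents do not support that. Section 9.3 ends participation and requires every enrolled subject to be accounted for, 9.5 keeps Implant subjects in the analyses, and Kaplan-Meier retains their time at risk. A calculation in which one event always vanishes would raise the exact type I error at the 12-month goal from 2.1% to 4.2% (n = 226), but no section provides for that.
- **A complication that prompts the review has already happened.** Section 19.1 requires reportable events after consent to be recorded, and 11.1.3.2 and 21.4 provide independent adjudication. An event recorded and adjudicated as system-related counts whatever follows. Section 10.10 also has a reportable event that is ongoing at study completion followed to resolution or closure before the End of Study form. That narrows the gap further, although it does not reach a complication that begins after withdrawal.
- **9.3 and 9.5 do not contradict each other.** Following Implant subjects as the protocol directs includes 9.3. This is an omission, not an inconsistency.
- **The eligibility item is not the only route.** The list is open, and an investigator's decision is a listed reason. Changing one item alone would leave a parallel path. This stands, and the fix has to cover it.

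Sensitivity to one event is also common to any performance-goal test near its boundary. It shows that a lost event could matter, not that one is likely. Analysis-set detail is deferred to the SAP, and the text of 11.1.3.3 is not in the available copy, so part of the answer may lie there.

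**Conclusion.** The point holds as a gap in follow-up. An implanted subject judged ineligible can be withdrawn with a working device and no required safety check, and any complication that begins afterwards goes uncounted. Bias towards meeting the goal follows only if the judgement is related to device tolerance, which is plausible but not stated. The 12-month endpoint is the one mainly exposed; the 30-day endpoint is hardly affected.

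The expected size is small and cannot be estimated, since nothing in the documents indicates how many implanted subjects might be found ineligible or what their later risk would be. The margin of 8 against 9 events of 227 rests on full follow-up of that number. The reversal in step 4 also assumes that the true count sits exactly at the boundary. Severity: minor.

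**What to change.** In 9.3, restrict the eligibility reason to Intent subjects. In 9.5, add wording such as: An Attempt or Implant subject later found not to have met the criteria is recorded as a protocol deviation. The subject is not withdrawn on that ground alone, nor under an investigator's decision resting on the same ground, except where consent is invalid or withdrawn. The subject completes the safety follow-up already defined for that classification and remains in the safety endpoint analyses.

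The cost is two short edits and continued EMR and telephone or virtual reviews for a few subjects, using contacts the protocol already schedules. No sample size, goal or test changes. The downside is that a few protocol violators stay in the safety set; they can be identified from the deviation records.

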9.4. Lost to Follow-Up

Any subject without a LATITUDE Clarity device transmission within 90 days prior to each required data collection point may indicate a potential lost to follow-up subject. The investigator or designee shall make efforts to contact the subject in order to re-establish successful LATITUDE Clarity device transmission. Subjects will be classified as lost to follow-up on the End of Study CRF after three documented failed attempts (by either telephone call or certified letter) to contact them are documented in the study file. *Note: the end of study date should be on or after last documented contact attempt.*

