Data Collection	Retention of Original Source Documentation
Information regarding the extended Holter monitor distribution, return, and data download and transmission	Study Site
Downloaded Holter monitor device raw data	Core lab and BSC
Extended Holter monitoring report and ECG strips	Core lab; a report copy is sent to BSC and Study Site
Reportable adverse events (as defined in Section 19.1) and protocol deviations, if applicable	Study Site

Table 10-5: 2-Month Holter Visit Source Documentation

10.8. 6-Month and 12-Month EMR Review (±30 days)

A review of each implanted subject's EMR must be performed at 6 months (\pm 30 days) and 12 months (\pm 30 days) post-ICM implant. Subjects are not required to visit the study site in-person. Reportable adverse events defined in Section 19.1 shall be collected. To supplement the EMR review, a phone call or virtual health visit to the subject must be attempted and documented to obtain adverse event information that may not be recorded in the EMR. If the subject is seen in-office that might be part of the standard-of care, then a phone call/virtual health visit is not required. It is not a study deviation if the subject cannot be reached by phone or virtual health visit despite attempts. In addition, any ICM reprogramming (to be documented throughout the study duration), arrhythmia diagnoses facilitated by the ICM, and the resulting arrhythmia treatments will be collected on the appropriate CRF. Site staff will confirm successful LATITUDE Clarity device transmission within the last 90 days to determine if the subject may be considered lost to follow-up.

Site is encouraged to perform the EMR review at the time of an in-office standard of care visit, if possible.

Print a copy of initial LATITUDE Clarity programming report to verify the time of the latest device transmission and print the applicable TSF for this visit. Data and source documentation requirements are summarized below in Table 10-6.

Data Collection	Retention of Original Source Documentation
ICM device transmission information	Study site
Information on arrhythmia diagnoses and related treatments since the LUXDx ICM implant	Study site
Reportable adverse events (as defined in Section 19.1) and protocol deviations, if applicable	Study Site

Table 10_6. 6.	and 12-Month	FMR Review	Source Documentation
1 abic 10-0. 0.	· and 12-month	THIN VENICA	Source Documentation

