10.9. LUX-Dx ICM Not in Service, Disabled, or Explanted

If the LUX-Dx ICM is permanently programmed off and not in service per investigator's decision, disabled due to device issue or malfunction, or explanted for any reason following a successful implant, the reasons for such actions must be recorded on the appropriate CRFs. Subjects with the LUX-Dx ICM disabled, but still implanted will be withdrawn from the study. If disabling of the ICM is a result of an adverse event, these subjects must be followed at least 30 days to assure any associated adverse events are followed to resolution or closure of the event with ongoing or chronic status before withdrawal. The safety check attempts must be made between 30 days and 60 days after the ICM is permanently programmed off or disabled. The withdrawal must occur after the resolution of all reportable adverse events and the completion of the safety check.

All subjects undergoing explant must be followed at least 30 days post explant to ensure any associated adverse events, related to explant or otherwise, are followed to resolution, or closure of the event with ongoing or chronic status. The safety check attempts must be made between 30 days and 60 days after the explant procedure. These subjects must be withdrawn from the study after satisfying the follow-up period of at least 30 days for the safety check.

Print any applicable TSF for this visit. Data and source documentation requirements are summarized below in Table 10-7.

Data Collection	Retention of Original Source Documentation
Not in service, disabling, and explant information	Study site
Reportable adverse events (as defined in Section 19.1) and protocol deviations, if applicable	Study Site

Table 10-7: Device Not in Service, Disabling, and Explant Source Documentation

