10.10. End of Study

The End of Study CRF must be completed following completion of the subject's 12-month $(\pm 30 \text{ days})$ EMR review, upon withdrawal of subject from the study, or upon subject's death. The subject's final status, including confirmation of a successful LATITUDE Clarity device transmission within the last 90 days, will be recorded on the End of Study CRF. There is no in-office visit requirement for this study procedure.

If a subject is experiencing a reportable adverse event at the time of study completion, the study site shall continue following the subject through resolution of the adverse event or closure of the adverse event as chronic or ongoing prior to completing the End of Study CRF.

Upon completion of the study, the subjects will be followed according to the site's standard of care.

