11.1.4.2. Statistical Methods

The ICM system-related complication-free rate at 12 months post-implant will be calculated using Kaplan-Meier methodology. The 97.5% one-side lower pointwise confidence limit of the ICM system-related complication-free rate will be calculated via log-log methodology and compared to the performance target of 93%. If the lower confidence limit exceeds 93% then the null hypothesis will be rejected.

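### Section 9.3 lets a site withdraw a reachable implanted subject when device transmission cannot be restored, giving up 12-month safety follow-up that could still be collected

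*Combined protocol and SAP*

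**What the plan says.** - **Withdrawal (9.3).** The open-ended list of reasons that may be recorded includes "Not able to re-establish device transmission after 90 days despite subject contact". Lost to follow-up is a separate entry.
- **Lost to follow-up (9.4).** A 90-day gap in transmission before a data collection point is a warning sign. Classification as lost comes only "after three documented failed attempts (by either telephone call or certified letter) to contact them".
- **Default for implanted subjects (9.5).** "These subjects are followed in accordance with the protocol and included in all applicable analyses".
- **How complications are found (10.8).** Each implanted subject's electronic medical record (EMR) must be reviewed at 6 and 12 months (±30 days). In addition, "a phone call or virtual health visit to the subject must be attempted and documented to obtain adverse event information", unless the subject is seen in the office. At the same reviews the site checks for a transmission in the last 90 days.
- **End of participation (10.10).** The End of Study form is completed after the 12-month review, "upon withdrawal of subject from the study, or upon subject's death".
- **Exits that carry a safety check (9.5, 10.9).** Attempt subjects, and subjects whose device is programmed off, disabled or explanted. For explant: "The safety check attempts must be made between 30 days and 60 days after the explant procedure".
- **Endpoint (11.1.4).** "The ICM system-related complication-free rate at 12 months post-implant will be calculated" by Kaplan-Meier. The one-sided 97.5% log-log lower limit is compared with 93%. Section 7.3 gives 226 as the number needed to power it.

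**The concern.** The transmission entry describes a subject who has been contacted but whose device still does not report. Device data serve the effectiveness objectives, so stopping their collection is reasonable. The chronic safety endpoint does not depend on them: a complication can be found in the medical record or by telephone whether or not the device transmits. Because withdrawal closes the subject's participation, this exit ends safety follow-up together with device-data collection, although only the second has become impossible.

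At stake is precision on a primary endpoint. A subject withdrawn at the 6-month review contributes nothing for months 6 to 12. If subjects who lose connectivity also had more later complications, the Kaplan-Meier estimate would be too favourable as well. The 30-day endpoint is not affected, since a 90-day silence cannot arise within it.

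**Working it through.** **Reading the sections together.** Section 9.4 reserves loss to follow-up for subjects who cannot be contacted, so the separate entry in 9.3 reaches subjects who can be. I looked for any rule that keeps such a subject under safety observation to month 12:

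- 9.5, 30-60 day check: only for subjects not successfully implanted.
- 10.9, 30-60 day check: device programmed off, disabled or explanted. Even if a silent device were classed as disabled by malfunction, an exit near month 6 would leave the check well short of month 12.
- 10.10, following an event to closure: only an event already present at study completion. New events are not sought.
- 10.8, review of each implanted subject: does not say that reviews continue after withdrawal.

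None does so.

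**The plan's figure.** The 226 cannot be reproduced, because the expected rate, power and any attrition allowance are not in the visible text. The decision rule at 226 can be. With 8 events and full follow-up:

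- S = 218/226 = 0.9646
- Greenwood sum V = 8/(226 × 218) = 0.0001624
- lower limit = S^exp(1.96·√V/|ln S|) = 93.05%, a pass.

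Nine events give 92.49%, a fail.

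**Effect of exits on precision.** Assumptions, none from the documents: true 12-month rate 97%; a share w of subjects (5% or 10%) exits at one time point, unrelated to complications; a share f of the 12-month hazard falls before that point.

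- q1 = 1 − 0.97^f and q2 = 1 − 0.97^(1−f)
- events before exit: d1 ~ Binomial(n, q1)
- events after exit: d2 ~ Binomial(n2, q2), with n2 = n − d1 − wn (wn rounded)
- S = (1 − d1/n)(1 − d2/n2)
- V = d1/[n(n − d1)] + d2/[n2(n2 − d2)]
- pass if the lower limit exceeds 93%; sum the probabilities over all d1, d2.

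The standard error rises by the square root of the ratio of expected V with and without exits. For w = 10% and f = 50%, q1 = q2 = 0.01511. Then n·V goes from 0.01535 + 0.01535/0.9849 = 0.03093 to 0.01535 + 0.01535/0.8849 = 0.03269, a rise of 2.8% in the standard error. Across f = 50-85% the rise is 0.4-1.3% (5% exits) or 0.9-2.8% (10%).

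Pass probability moves in jumps because events are whole numbers, so I averaged over n = 216 to 240, where it is 70.7% without exits:

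| Exit time | Early hazard share | Loss, 5% exits | Loss, 10% exits |
|---|---|---|---|
| Month 6 | 50% / 70% / 85% | 0.53 / 0.20 / 0.03 points | 2.73 / 1.18 / 0.41 points |
| Near month 9 | 75% to 92.5% | about 0.0-0.1 points | about 0.2-0.9 points |

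Two exit times are shown because the 90 days in 9.3 can be read as the silence itself, found at the 6-month review, or as a further 90 days of failed attempts after it.

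If more subjects are analysed, the loss is at most about 0.2 points: at n = 600 with 60 exits, 99.48% falls to 99.25% at worst; at n = 827 with 83 exits, 99.97% to 99.95%. At a true rate of 96% and n = 600 it could reach 1.8 points (87.25% to 85.5%).

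**Bias, purely hypothetical.** Take 10% exits at month 6, f = 50%, a Kaplan-Meier value of 97%, and a three-fold later hazard in those who left. The true rate is 0.9 × 0.97 + 0.1 × 0.97^(0.5 + 3 × 0.5) = 0.873 + 0.0941 = 0.9671, an overstatement of 0.29 points. With f = 70% or 85% it is 0.18 or 0.09 points. With equal hazard it is zero.

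**The case against.** The strongest reply is that 9.3 is a list of reasons to record, not a follow-up rule. It sets no duty to withdraw, while 9.4, 9.5 and 10.8 all point to restoring contact and keeping the subject. That stands, and a reader who infers that the plan requires withdrawal of silent-device subjects goes beyond the text. It does not close the gap: sites may treat the same subject differently, and nothing continues follow-up once the exit is used.

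Second, remote follow-up through the patient app is an inclusion criterion, so allowing exit when it fails is a coherent choice. That justifies ending device-data collection, not safety review by other means.

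Third, the statistical analysis plan, to which 11.2.1 defers the analysis sets, or an unseen attrition allowance may cover such exits. Either could soften the effect on power or set a censoring rule. Neither can recover follow-up that was never collected.

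Fourth, the same list allows exit after implant of an active therapy device even if the monitor stays in place, with a similar loss of safety data. That is fair; the point here is limited to transmission failure.

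**Conclusion.** The gap is real but modest: a permitted exit that discards obtainable follow-up for a primary safety endpoint. Its frequency is unknown and may be zero. The smoothed losses tabulated above are the fair measure of size. They rest on assumed exit shares, exit times, hazard timing and a 97% true rate, and on about 226 subjects being analysed, which the visible text does not settle.

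Two stronger readings are not supported:

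- **A large loss of power at the planned size.** At exactly n = 226 the pass probability drops from 76.0% to 66.2% with 11 exits (f = 50%), but only to 67.8% with 23. Losing more subjects appears to cost less. This is a whole-number artefact, because 8 events pass by only 0.05 points; figures at n = 230 have the same problem. Neither is evidence of lost information.
- **An upward-biased 12-month rate.** This requires lost connectivity to be associated with later complications. The documents neither show nor exclude that.

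It is worth considering as a cheap improvement and is not a flaw that undermines the endpoint.

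**What to change.** In 9.3, state that failure to re-establish transmission ends device-data collection only, and that consenting, reachable subjects stay in the scheduled 6- and 12-month record review and contact for adverse events (10.8) and in the chronic Kaplan-Meier risk set.

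The cost is one sentence, the ethics review that any amendment needs (16.3), and a few extra record reviews and calls at time points already scheduled. Affected subjects stay in the study up to about 6 months longer. No new visit, procedure or staff is needed.
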